Because of the high prevalence of cardiovascular morbidity and mortality in CKD patient, we need a better understanding of the mechanism for treatment strategy. Metabolomics was used in identifying new biomarkers of CKD such as acylcarnitines, glycerolipids, dimethylarginines and metabolites of tryptophan. C-mannosyl tryptophan and pseudouridine have better performance than creatinine in CKD stratification (Hocher & Adamski, 2017). Inflammation status was significantly reduced by treatments. There was no significant difference between treatments (Moutzouri et al., 2013). Endothelial dysfunction secondary to the pro-inflammatory and pro-oxidative state caused by Oxidative stress (OS) causing endothelial dysfunction secondary to the pro-inflammatory and pro-oxidative was observed in CKD. However, how hypolipidemic agents impact on Oxidative stress is still not clear. Tryptophan (Trp) degradation via indoleamine (2,3)-dioxygenase (IDO), with consequent increased in kynurene (Kyn) concentrations, has been considered as a marker of immune system activation (Schefold et al., 2009). The effect cholesterol-lowering treatment on oxidative and inflammation parameters in CKD might be mediated by restoration of antioxidant taurine concentrations, suggesting that amelioration of both oxidative and inflammation status in CKD patients could be partly explained by the cholesterol-lowering effects (Zinelli et al., 2015).

In clinical practice, physicians always concern the effects and safety before giving the prescription. However, despite the high frequency of statin treatment, only 1/3 of CKD patients achieved the LDL-C goal. Whether high-dose of statins mono-therapy is more effective in LDL-C lowering is still unclear, but are associated with a high rate of hepatotoxicity, myopathy.

Lowering LDL-C with statin mono-therapy and statin/ezetimibe combination reduces the risk of CVD in population without kidney disease. Which Cholesterol-lowering therapies are suitable for stage 3,4 CKD patients in term of e-GFR reduction and side effects? There is no data related to this field in the Vietnamese CKD population. Thus, more advanced lipid-lowering therapies and a better understanding of the mechanism is needed for treatment strategy of hyperlipidemia in Vietnamese patients with CKD. The following research questions need to be addressed:

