2.9. Recommendations for treatment goals for low-density lipoprotein-cholesterol (Catapano et al., 2016)

Recommendation	Class of recommendation	Level of evidence
In patients at VERY HIGH CV risk, an LDL-C goal of <1.8 mmol/L (70 mg/dL) or a reduction of at least 50% if the baseline LDL-C is between 1.8 and 3.5 mmol/L (70 and 135 mg/dL) is recommended.	I	B
In patients at HIGH CV risk, an LDL-C goal of <2.6 mmol/L (100 mg/dL), or a reduction of at least 50% if the baseline LDL-C is between 2.6 and 5.2 mmol/L (100 and 200 mg/dL) is recommended.	I	B
In subjects at LOW or MODERATE risk, an LDL-C goal of <3.0 mmol/L (<115 mg/dL) should be considered	IIa	C

2.10. Lipid Measurement in Adults with CKD. (Sarnak et al., 2015). 2013 KDIGO Clinical Practice Guidline for Lipid management in CKD

1.1. In adults with newly identified CKD (including those treated with chronic dialysis or kidney transplantation), we recommend an evaluation with a lipid profile (total cholesterol, LDL cholesterol, HDL cholesterol, triglycerides). (1C)

1.2. In adults with CKD (including those treated with chronic dialysis or kidney transplantation), follow-up measurement of lipid levels is not required for the majority of patients. (Not Graded)

2.1.1. In adults aged \geq 50 years with eGFR $<$ 60 ml/min/1.73 m² but not treated with chronic dialysis or kidney transplantation (GFR categories G3a-G5), we recommend treatment with a statin or statin/ezetimibe combination. (1A)

2.1.2: In adults aged \geq 50 years with CKD and eGFR \geq 60 ml/min/1.73 m² (GFR categories G1-G2), we recommend treatment with a statin. (1B)

2.2: In adults aged 18-49 years with CKD but not treated with chronic dialysis or kidney transplantation, we suggest statin treatment in people with one or more of the following (2A):

- known coronary disease (myocardial infarction or coronary revascularization)
- diabetes mellitus
- prior ischemic stroke
- estimated 10-year incidence of coronary death or non-fatal myocardial infarction > 10%

2.3.1: In adults with dialysis-dependent CKD, we suggest that statins or statin/ezetimibe combination not be initiated. (2A)

2.3.2: In patients already receiving statins or statin/ezetimibe combination at the time of dialysis initiation, we suggest that these agents be continued. (2C)

2.4: In adult kidney transplant recipients, we suggest treatment with a statin. (2B)

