4.2.2. Exclusion Criteria

- In adults with dialysis-dependent CKD
- Heart failure (New York Heart Association class III or more)
- Previous or concomitant treatment with corticoids, statin, immunosuppressive agents, vitamin B6, B12, folate
- Pregnancy
- Patients who do not agree to participate the research
- Patients are unable to fully understand the purposes/risks of the study and to provide a written informed consent

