4.2.3. Criteria for control

- 30 aged, sex-matched subject
- Do not have history of diabetes, hypertension, cardiovascular or cerebrovascular disease, renal failure, blood dyscrasias, cancer, retinal vascular disorders
- Current medication with vitamin B6, B12, or folic acid

4.3. Place:

- In Viet Nam: Internal examination room, internal department, Department of Biochemistry of Hue University Hospital.

- In Italy: Department of Biochemistry of Sassari University Hospital

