4.6. Procedure

- Potentially eligible patients attended a screening visit in an internal examination room or internal department of Hue University Hospital for medical history and other eligibility criteria checked.

- Fasting blood samples will be taken for local laboratory assays lipid profile, proteinuria, urea and creatinine, creatine kinase, SGOT, SGPT, total blood count, total haemostasis test

- If the patient satisfies the including criteria, written informed consent obtained 30 enrolled patients will be randomized into 3 groups and will receive one of 3 lipid-lowering therapies at the baseline and continue for 12 months

Group 1: (10 participants) receive 40 mg/day simvastatin (patient No 1, 4, 7...)

Group 2: (10 participants) receive ezetimibe/simvastatin 10/20 mg/day: (patient No 2, 5, 8...)

Group 3: (10 participants) receive ezetimibe/simvastatin 10/40 mg/day: 10/40: (patient No 3, 6, 9...)

- Patients will follow the treatment for 12 months and will be seen in the study clinics for routine follow-up checks and blood test at 4, 8, and 12 months.

- At each follow-up time, study treatment will be continued, unexplained muscle pain and non-study treatment recorded.

Patients are asked for an unscheduled visit if they want to have any additional review.

- If patients are unable or unwilling to attend the follow-up checks, ask them if they have any serious adverse events.

- The blood samples will be sent to Biochemical Department of Sassari University for oxidative stress indices and Tryptophan degradation indices every 4 months.

5. Biochemical analysis

- Serum Creatinine, GFR, urine protein, lipid profile, SGOT, SGPT, CK (Total Cholesterol, LDL-C, HDL-C, TG): Will be done in Hue University hospital/Hue Central Hospital.

+ Total Cholesterol, LDL-C, HDL-C, and TG were measured by enzymatic methods using commercial kits (Boehringer-Mannheim, Mannheim, Germany): Patients must fast for at least 12 hours before the test

+ Serum CK levels were measured by using a fully automated biochemical analyzer (Abbot).

+ Proteinuria

+ Serum urea, creatinine

+ Total cells blood count

+ Total hemostasis test

[Time Frame: at baseline and 4, 8, 12 months of treatment]

- Serum concentrations of Oxidative stress indices (MDA, All/UA, Taurine), Trp degradation indices (Kyn, Trp, Kyn/Trp ratio): Will be done in Sassari University hospital.

MDA, All/UA ratio, taurine, Kyn, Trp were determined by capillary electrophoresis UV detection.

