STATISTICAL ANALYSIS PLAN

LIPID-LOWERING REGIMES IMPROVE OXIDATIVE STRESS, TRYPTOPHAN DEGRADATION IN HYPERCHOLESTEROLEMIA CKD PATIENTS

Date of review: 05th May, 2018

All results will be expressed as mean values (mean SD) or median values (median and range).

The statistical differences between the mean laboratory test results patients and control group will be analyzed by ANOVA one-way statistical analysis or by Student's t-test (with Kolmogorov-Smirnov for normality).

The statistical differences in the effect of each therapy on laboratory mean values will be evaluated by one way repeated measure ANOVA with Bonferroni correction or Dunnet T3 correction, if appropriate.

To compare the differences in the median values of laboratory tests between 3 groups, ANOVA one-way will be applied. If there are statistical differences between 3 groups, we will use deeply ANOVA one-way test to analyze which group is different from another group (with Bonferroni if Levene test ≥ 0.05 or Dunnet T3 if Levene test < 0.05).

Correlation analysis between variables will be performed by Pearson's correlation or Spearman's correlation as appropriate.

Statistical analysis will be performed by using SPSS for Windows, version 20.0 (IBM Corporation; Armonk, NY, USA).

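### The control criteria in 4.2.3 list current vitamin B6, B12 or folic acid use without a negation and, even read as an exclusion, do not match the patient medication exclusions in 4.2.2 (minor)

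*Protocol*

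**What the plan says.** Protocol section 4.2.3 has three bullets for controls. The first asks for 30 age- and sex-matched people. The second carries its own negation and concerns disease only: "Do not have history of diabetes, hypertension, cardiovascular or cerebrovascular disease, renal failure", followed by blood dyscrasias, cancer and retinal vascular disorders. The third reads in full "Current medication with vitamin B6, B12, or folic acid". No other control criterion concerns medication.

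For patients, section 4.2.2 lists as an exclusion "Previous or concomitant treatment with corticoids, statin, immunosuppressive agents, vitamin B6, B12, folate".

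The SAP uses the controls in one named analysis: "The statistical differences between the mean laboratory test results patients and control group will be analyzed by ANOVA one-way" or by Student's t-test. It names no adjustment for medication. It also does not say which patient sample is meant, although section 5 of the protocol has patients sampled repeatedly ("Time Frame: at baseline and 4, 8, 12 months of treatment").

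**The concern.** An eligibility rule is applied as it is printed. Someone recruiting controls from 4.2.3 could take the third bullet as a requirement and enrol people on vitamins that would have kept a patient out of the study. If it is read as an exclusion instead, the two groups still face different medication rules.

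What is at stake is the patient-control comparison of laboratory values, including the oxidative-stress and tryptophan markers. Medicines barred in one group and allowed in the other can contribute to a difference that would then be credited to kidney disease. The protocol mentions recording of non-study treatment only within patient follow-up (section 4.6) and is silent on controls. As planned, then, the exposure could be neither ruled out nor examined afterwards.

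**Working it through.** **Item-by-item comparison.** The plan gives no figure to reproduce here, so the check starts from the two lists.

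| Medicine | Patients (4.2.2) | Controls, as printed (4.2.3) | Controls, negation restored |
|---|---|---|---|
| Vitamin B6, B12, folate | Excluded, previous or concomitant | Current use listed as a criterion | Excluded, current use only |
| Statins | Excluded, previous or concomitant | Not mentioned | Not mentioned |
| Corticoids | Excluded, previous or concomitant | Not mentioned | Not mentioned |
| Immunosuppressive agents | Excluded, previous or concomitant | Not mentioned | Not mentioned |

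As printed, none of the four items matches. With the negation restored, only the vitamin item does, and only for current use.

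**Do the disease exclusions close the gap?** Only in part. Barring diabetes, hypertension, cardiovascular and cerebrovascular disease makes statin use in controls less likely. Hypercholesterolaemia is not barred, however. The Background refers to statin treatment outside kidney disease ("Lowering LDL-C with statin mono-therapy and statin/ezetimibe combination reduces the risk of CVD in population without kidney disease"), and section 2.9 gives an LDL-C target even at lower risk ("In subjects at LOW or MODERATE risk, an LDL-C goal of <3.0 mmol/L (<115 mg/dL) should be considered"). Statin use in a control is therefore possible. Nothing in the documents shows that it is common.

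**Size.** If k of the 30 controls are exposed and the medicine shifts a marker by d SD in users, the bias in the patient-control difference is (k/30) × d. The documents give neither k nor d. On the effect of lipid-lowering drugs on oxidative stress the Background says "how hypolipidemic agents impact on Oxidative stress is still not clear". Neither size nor direction can be derived.

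**Illustration only: every k and d below is an assumption.** Take 30 patients and 30 controls as independent groups with a common SD.

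- SE = √(1/30 + 1/30) = 0.258 SD; t critical value (58 df) = 2.002.
- Coverage of the 95% interval for the difference without these medicines follows from a non-central t distribution with non-centrality bias/SE.
- k = 1, d = 0.2: bias = 1/30 × 0.2 = 0.007 SD, coverage 95.0%.
- k = 3, d = 0.5: bias = 3/30 × 0.5 = 0.05 SD, coverage 94.6%.
- k = 3, d = 0.8: bias = 3/30 × 0.8 = 0.08 SD, coverage 93.9%.
- Coverage falls to 90% at a bias of 0.171 SD (0.663 SE). That needs k = 30 × 0.171/d: 6.4 controls at d = 0.8, 10.3 at d = 0.5 and 25.7 at d = 0.2.

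With few exposed controls the effect on the comparison is negligible; it becomes visible only when many are exposed. If the vitamin bullet were followed literally, k/30 = 1 and the bias would equal d. The documents give no d for the vitamins, so no figure is claimed for that case.

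**The case against.** The strongest reply is that this is a drafting slip. The bullet follows one that opens with a negation and names the vitamins that exclude patients, so most readers would take it as an exclusion. That is the likeliest reading, and it is the main reason the point is minor. It does not remove the need to correct the text, because the printed rule says the opposite, and the narrower time window and the three unlisted drug classes remain either way.

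Second, evidence that controls would take the unlisted drugs is thin. The Background sentence concerns benefit rather than frequency of use, the low-to-moderate-risk row in section 2.9 names no drug, and nothing at all is offered for corticoids or immunosuppressive agents. This stands: exposure is a possibility, not a finding.

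Third, the groups differ in comorbidity by design. Patients may have diabetes or coronary disease and take other medicines, so aligning four items will not produce a comparison free of medication effects. This also stands. Alignment removes one avoidable source of difference and leaves the rest.

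Fourth, the illustration treats the groups as independent although controls are age- and sex-matched, and 90% coverage is an arbitrary threshold. A paired analysis would change the SE and the counts. The figures show orders of magnitude only.

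A reader might go further and infer that the controls are vitamin users by design, or that the treatment results are compromised. The documents do not support either. Nothing gives a reason for wanting vitamin users as controls. The comparison of the three regimens does not use the controls, and neither numbered objective in section 3 mentions them.

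**Conclusion.** The inconsistency is real and of minor severity. As printed, the vitamin bullet in 4.2.3 contradicts the purpose of 4.2.2. With the presumed negation restored, 4.2.3 is still narrower in its time window and in the medicines covered. The unadjusted patient-control comparison could therefore be confounded. That this confounding is present, large or in a known direction would be a stronger claim than the documents allow, since they give neither frequency of use in controls nor the effect of these medicines on the markers.

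The conclusion that the bias is small if few controls are exposed rests on the assumed range of 1 to 3 exposed controls and effects of 0.2 to 0.8 SD (bias 0.007 to 0.08 SD). It would not carry over to a control group recruited by the literal wording. The unspecified patient sample in the SAP is a separate gap in the same comparison. It is worth closing in the same edit but adds nothing to the severity of this point.

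**What to change.** 1. **Protocol 4.2.3.** Reconcile it with 4.2.2: word the vitamin bullet as an exclusion, and apply to controls the same medicine list (corticoids, statins, immunosuppressive agents, vitamin B6, B12, folate) and the same time window as to patients. Define that window once for both groups.
2. **Data collection.** Record each control's medication when blood is taken.
3. **SAP.** State that the patients' baseline, pre-treatment samples are the ones compared with controls. Samples at 4, 8 and 12 months are taken on study drug, and all three regimens in section 4.5 contain simvastatin.
4. **Controls already recruited.** Report how many use the listed medicines. Repeat the comparison without them only if enough unexposed controls remain; otherwise report the confounding as a limitation. If the bullet was followed literally, no controls would remain and only the second course is open.

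**Cost.** A short rewording of 4.2.3, one data field and one SAP sentence. The study period opens in November 2017 and the protocol's review date is May 2018, so medication histories may also have to be obtained from controls already enrolled; the documents do not say how many there are. Under the same independent-groups assumption, leaving out 3 controls raises the SE to √(1/30 + 1/27) = 0.265 SD (+3%), and leaving out 6 raises it to √(1/30 + 1/24) = 0.274 SD (+6%).

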4.4. Time: 3 years (From November 2017 to November 2020)

4.5. Medication:

- Group1: simvastatin 40mg/day 12 months
- Group2: EZE/simvastatin (10/20) mg/day 12 months
- Group3: EZE/simvastatin (10/40) mg/day 12 months

4.6. Procedure

- Potentially eligible patients attended a screening visit in an internal examination room or internal department of Hue University Hospital for medical history and other eligibility criteria checked.

- Fasting blood samples will be taken for local laboratory assays lipid profile, proteinuria, urea and creatinine, creatine kinase, SGOT, SGPT, total blood count, total haemostasis test

- If the patient satisfies the including criteria, written informed consent obtained 30 enrolled patients will be randomized into 3 groups and will receive one of 3 lipid-lowering therapies at the baseline and continue for 12 months

Group 1: (10 participants) receive 40 mg/day simvastatin (patient No 1, 4, 7...)

Group 2: (10 participants) receive ezetimibe/simvastatin 10/20 mg/day: (patient No 2, 5, 8...)

Group 3: (10 participants) receive ezetimibe/simvastatin 10/40 mg/day: 10/40: (patient No 3, 6, 9...)

- Patients will follow the treatment for 12 months and will be seen in the study clinics for routine follow-up checks and blood test at 4, 8, and 12 months.

- At each follow-up time, study treatment will be continued, unexplained muscle pain and non-study treatment recorded.

Patients are asked for an unscheduled visit if they want to have any additional review.

- If patients are unable or unwilling to attend the follow-up checks, ask them if they have any serious adverse events.

- The blood samples will be sent to Biochemical Department of Sassari University for oxidative stress indices and Tryptophan degradation indices every 4 months.

5. Biochemical analysis

- Serum Creatinine, GFR, urine protein, lipid profile, SGOT, SGPT, CK (Total Cholesterol, LDL-C, HDL-C, TG): Will be done in Hue University hospital/Hue Central Hospital.

+ Total Cholesterol, LDL-C, HDL-C, and TG were measured by enzymatic methods using commercial kits (Boehringer-Mannheim, Mannheim, Germany): Patients must fast for at least 12 hours before the test

+ Serum CK levels were measured by using a fully automated biochemical analyzer (Abbot).

+ Proteinuria

+ Serum urea, creatinine

+ Total cells blood count

+ Total hemostasis test

[Time Frame: at baseline and 4, 8, 12 months of treatment]

- Serum concentrations of Oxidative stress indices (MDA, All/UA, Taurine), Trp degradation indices (Kyn, Trp, Kyn/Trp ratio): Will be done in Sassari University hospital.

MDA, All/UA ratio, taurine, Kyn, Trp were determined by capillary electrophoresis UV detection.

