2.4. Oxidative stress, inflammation and cardiovascular disease in chronic renal failure

Traditional risk factors, as well as additional nontraditional risk factors, can directly damage the kidney. Some studies have shown the relationship between oxidative stress and inflammatory biomarkers. Some clinical studies indicated an inverse

correlation between oxidative stress status and estimated glomerular filtration rate (eGFR) (Stevens et al., 2013).

Different mechanisms could explain the oxidative stress increase in CKD. Some conditions of CKD patients such as advanced age, diabetes, hypertension, lower levels intake of the antioxidant vitamin, and failure of ROS clearance in renal function are related to the increase of oxidative stress and progression of CKD (Meenakshi Sundaram, Nagarajan, & Manjula Devi, 2014)

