2.12. Simvastatin

- Treat with statins for 1-2 weeks, up to 4-6 weeks, and maintain during long-term treatment.
- Simvastatin largely excreted in the feces. Approximately 10-15% of the drug excreted by the kidney
- Dosage is 5-80 mg/day, in the evening.
- No dosage adjustment is needed in the elderly
- **Contraindications of Simvastatin:**
 - + Active liver disease or unexplained persistent elevations of serum transaminases

- + Pregnancy and lactation
- + Concomitant administration of potent CYP3A4 inhibitors (e.g. itraconazole, ketoconazole, posaconazole, HIV protease inhibitors (e.g. nelfinavir), erythromycin, clarithromycin, telithromycin, and nefazodone)
- + Concomitant administration of gemfibrozil, ciclosporin, or danazol.
- **Unexpected effects of Simvastatin and how to manage unexpected effects**
 - + **Myopathy:** The risk of myopathy is related to dose. In a clinical trial of 41,413 patients treated with simvastatin, 24,747 patients (about 60%) with an average follow-up of at least 4 years, the incidence of myopathy was approximately 0.03%, 0.08% and 0, 61% at doses of 20, 40 and 80 mg/day, respectively.
 - If the patients have muscle aches, weakness or cramps, do CK test. If CK increases (> 5 times) discontinue treatment, re-assess levels within 5 to 7 days.
 - If the muscular symptoms are severe and cause daily discomfort, even if the CK levels are < 5 times normal, consider stopping treatment.
 - + **Elevated liver enzymes:** Continuous elevations (up to > 3 times) liver enzymes have occurred in some patients receiving simvastatin.
 - When simvastatin is discontinued, the level of transaminase usually decreases gradually down to the pre-treatment level.

+ **Diabetes Mellitus**

Some evidence suggests that statins as a class raise blood glucose and in some patients, at high risk of future diabetes, may produce a level of hyperglycemia where formal diabetes care is appropriate. This risk, however, is outweighed by the reduction in vascular risk with statins and therefore should not be a reason for stopping statin treatment.

+ Other side effects: Dizziness, fainting, fast or irregular heartbeat,...

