4. METHODOLOGY

4.1. Study design: A prospectively study with clinical trials, 12 months follow up.

4.2. Subject: 30 patients with hypercholesterolemia (LDL-C), stage 3-4 Chronic Kidney Disease, not receiving dialysis and 30 control participants (sex, age-matched)

4.2.1. Inclusion Criteria:

30 patients with following criteria

- CKD in the 3,4 stage (e-GFR: 15-60 ml/min/1.73 m²)
- Presence of proteinuric CKD defined as creatinine clearance >20 ml/min/1.73 m² combined with urinary protein excretion rate >0.3 g/24 h
- LDL cholesterol concentration > 100 mg/dl (2,59 mmol/l)
- Age:
 - + ≥ 50 years old but not treated with chronic dialysis or kidney transplantation
 - + In adults aged 18-49 years with CKD but not treated with chronic dialysis or kidney transplantation, we suggest statin treatment in people with one or more of the following:
 - known coronary disease (myocardial infarction or coronary revascularization)
 - diabetes mellitus
 - prior ischemic stroke
 - estimated 10-year incidence of coronary death or non-fatal myocardial infarction > 10%

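### Raised blood glucose is one of three headed simvastatin effects in section 2.12, but no glucose or HbA1c is scheduled, so the side-effect comparison in objective 2 cannot cover it

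*Protocol*

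**What the plan says.** Protocol section 2.12 has a list titled "Unexpected effects of Simvastatin and how to manage unexpected effects". It contains three headed items: myopathy, elevated liver enzymes and diabetes mellitus. Under the third it says: "Some evidence suggests that statins as a class raise blood glucose and in some patients" at high risk of future diabetes the level may call for diabetes care. It adds that vascular benefit outweighs this risk and that it is no ground for stopping a statin. A closing line begins "Other side effects: Dizziness, fainting, fast or irregular heartbeat".

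Section 3, objective 2, compares simvastatin alone with the two ezetimibe/simvastatin regimens on several outcomes, side effects among them, with no restriction on which side effects. Research question 4, at the end of section I, is narrower and asks about muscle problems and the hepatic enzyme profile.

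Section 4.6 gives the local laboratory list: "Fasting blood samples will be taken for local laboratory assays lipid profile, proteinuria, urea and creatinine, creatine kinase, SGOT, SGPT, total blood count", then haemostasis tests. Section 5 opens its local list with "Serum Creatinine, GFR, urine protein, lipid profile, SGOT, SGPT, CK" and sets the times as baseline and months 4, 8 and 12, with a fast of at least 12 hours for the lipid tests. The second laboratory measures "Serum concentrations of Oxidative stress indices (MDA, All/UA, Taurine), Trp degradation indices (Kyn, Trp, Kyn/Trp ratio"). Section 4.6 also has staff record unexplained muscle pain and non-study treatment at each visit, and ask patients who cannot or will not attend about serious adverse events. The SAP lists no safety variables.

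**The concern.** The protocol names three simvastatin effects under their own headings and schedules a laboratory measure for two of them. It then promises a side-effect comparison between regimens that differ in simvastatin dose (40 mg, 20 mg and 40 mg a day, by section 4.5) without saying that the third effect is left out. A trial run as written could report on side effects by arm when one effect it had itself identified was never measured. A reader of that report could take silence on glucose as absence of an effect. A baseline glucose cannot be reliably reconstructed once treatment has started, so the decision has to be made before a patient is dosed.

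**Working it through.** The plan gives no figure to reproduce on this point. The check sets the list of effects against every assay list and visit procedure.

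**Headed effects in section 2.12 against planned measurement**

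| Headed effect | Laboratory measure (4.6, section 5) | Scheduled time points | Other capture (4.6) |
|---|---|---|---|
| Myopathy | CK | 4 of 4 | Unexplained muscle pain recorded at visits |
| Elevated liver enzymes | SGOT, SGPT | 4 of 4 | None specific |
| Diabetes mellitus / raised glucose | None | 0 of 4 | Indirect only: record of non-study treatment |

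Time points: 1 baseline + 3 follow-up (months 4, 8 and 12) = 4. I take the fasting screening sample in 4.6 as the baseline sample of section 5.

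Headed effects with a laboratory measure: 2 of 3. Without: 1 of 3.

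**Search for glucose elsewhere.** Neither the local list in 4.6, the local and second-laboratory lists in section 5, the DNA-methylation item that follows them, nor the SAP contains glucose or HbA1c. In the study text, blood glucose appears only in the risk statement of section 2.12.

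**Could the effect be seen another way?** A newly started glucose-lowering drug might show up under non-study treatment, and a serious event might be reported by a patient who does not attend. Neither shows a rise in glucose that leads to no treatment, and neither gives a value to compare between arms.

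**Size of the remedy.** 30 treated patients × 4 scheduled samples = 120 assays. Section 5 already requires fasting for the lipid tests at the same times, so no extra visit or needle is needed.

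**What the added data could show.** There are 10 patients per arm (4.6). For a two-sided t-test at the 5% level comparing two arms, 80% power needs a true difference of about 1.32 SD. With a Bonferroni correction for three pairs (0.05 / 3 = 0.0167) it is about 1.57 SD. Power for a difference of 0.5 SD at the 5% level is about 19%. These figures assume normal data, equal variances and no dropout. The added data would therefore be descriptive.

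**The case against.** The strongest defence is that the omission matches the protocol's own safety question. Research question 4 asks about muscle and liver, and CK, SGOT/SGPT and recorded muscle pain answer exactly that. Section 2.12 is literature review, not a monitoring plan. It also treats the glucose effect differently from the muscle effect, calling it outweighed by vascular benefit. Dizziness, fainting and irregular heartbeat are named there too, without any specified capture, so the count of three depends on taking only the headed items. Much of this stands: the omission may well be deliberate, and the point is minor. It does not settle the matter, because objective 2 is worded without the limit in question 4, the protocol gives no reason for leaving glucose out, and the remark in 2.12 concerns stopping treatment rather than measuring.

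It is also fair that 10 patients per arm cannot support a dose comparison on glucose. The same is true of CK and the liver enzymes, which are measured all the same.

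Two stronger readings are tempting and should be resisted.

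- A reader might infer that the efficacy results are compromised, because section 2.4 says "Some conditions of CKD patients such as advanced age, diabetes, hypertension" and others are related to increased oxidative stress. That passage concerns diabetes as a condition. It does not say that a change in glucose over 12 months moves MDA, All/UA or Kyn/Trp. If simvastatin itself raised glucose, that would lie on the treatment's own pathway, and the comparison of regimens would still estimate the total effect.
- A reader might infer that the trial deliberately enrols people at risk of this effect because diabetes is a route of entry. In section 4.2.1 diabetes is one of four qualifying conditions, and only for ages 18–49. Older patients need none of them, although diabetes excludes no one. Patients who enter because they already have diabetes cannot newly develop it, so this route does not show enrichment for the risk that 2.12 describes.

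**Conclusion.** The point holds as a gap in the completeness of safety measurement. One of three headed simvastatin effects has no scheduled measurement at any of four time points in any of the 30 patients, while the other two are measured at all four. A rise in glucose could not be seen or compared by arm; at most, a new glucose-lowering prescription might come to light. The gap invalidates no planned comparison of lipids, oxidative stress or tryptophan indices, and closing it would not produce a powered test. The conclusion rests on reading objective 2 as unrestricted. If the sponsor meant it to be bounded by research question 4, the remaining fault is that the protocol does not say so. This is a low-cost improvement that is worth making.

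**What to change.** Add fasting plasma glucose to the local panel in section 4.6 and section 5 at baseline and months 4, 8 and 12, using the fasting blood already drawn. Tabulate baseline diabetes status by arm from the medical history taken at screening. Add a line to the SAP stating that change in glucose from baseline will be reported by arm, descriptively and without a formal test.

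If the sponsor prefers not to measure glucose, word objective 2 and its reporting so that the side-effect conclusion is limited to muscle and liver effects, and give the reason.

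The cost is about 120 routine assays, with no new visit and no new needle. The limitation to state openly is that 10 patients per arm give description only. No stopping or treatment rule is proposed.
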